6.3.4 Subject Withdrawal

Subjects may withdraw from the investigation at any time without providing a reason. Subjects will not be penalized nor lose any benefits to which they are otherwise entitled should they choose to withdraw. The investigator may also choose to withdraw a subject if he or she feels that this is in the subject's best interest. This information is included in the subject ICF.

A withdrawn subject's ongoing follow-up treatment will not be compromised in any way subsequent to withdrawal. If a subject elects to withdraw prior to completing the trial, an effort will be made to collect final data and information regarding the reason for withdrawal. Subject withdrawal information will be recorded on the appropriate electronic case report form (Completion/Discontinuation eCRF).

6.3.5 Subject Death

If a subject death occurs during the study, the Sponsor and Sponsor representative should be contacted immediately and the applicable regulatory authorities and IRBs notified as required by the regulations (also see Section 10.4.2). The subject death should be documented on the Adverse Event eCRF and the Completion/Discontinuation eCRF. Ancillary information regarding the subject's death and its relationship to the investigational product, such as autopsy reports, should also be provided if available.

6.4 Procedures

6.4.1 *Subject Registration and Numbering*

Subjects who meet the preoperative eligibility criteria will be asked to sign and date the current IRB-approved ICF. Informed consent must be obtained for all subjects who are potential study candidates before any study-specific tests or procedures are performed. Upon giving written informed consent, all subjects will be assigned a unique four digit subject identification number according to the order of screening. The first two digits will identify the investigative site; the remaining two digits identify subjects in order of screening. The two sets of digits will be separated by a dash.

Study personnel should explain that even if a subject agrees to participate in the study, they may not meet the eligibility criteria for enrollment in the study. During the intraoperative period, only those who meet the intraoperative eligibility criteria will be enrolled into the study.

After the subject has agreed to participate in the study and signed the ICF, the following information will be documented on the Subject Screening eCRF:

- Subject gender;
- Subject date of birth;
- Subject ethnicity and race; and
- Confirmation of all preoperative inclusion and exclusion criteria.

The Laboratory eCRF will be completed as applicable. Sample CRFs are provided in Appendix E.

6.4.2 *Preoperative Evaluations*

The following baseline data will be taken and recorded and will occur no more than 1 month (30 days) prior to surgery:

- Physical exam, including the subject's height, weight, temperature, diastolic and systolic blood pressure;
- Indication for surgery, reoperation information, and concomitant procedures;
- Use of any blood modifiers, insulin or blood sugar lowering and/or reversal drugs;
- Complete blood count and coagulation status (platelet count, PTT, INR, and fibrinogen) and Complement C3;
- Medical history, including smoking habits, use of oral contraceptives, diabetes and type, if applicable, and the presence of any malignancies (including if the subject has undergone chemotherapy within the last 6 months and date of last treatment, if applicable, and if the subject is undergoing surgery for this malignancy); and
- Thromboembolism Risk Assessment.

NOTE: For subjects with more than one laboratory report available, the values most proximal to the time of implant of the test or control articles should be evaluated to determine eligibility.

This information will be recorded on the Preoperative eCRF and Laboratory eCRF. The Blood Modifiers/Blood Sugar Lowering eCRF should be completed as applicable.

6.4.3 *Intraoperative Procedures and Evaluations*

All subjects will undergo the same intraoperative investigational evaluations unless otherwise stated. Intraoperative is defined as the time interval from when the subject enters the surgical suite until the subject exits the surgical suite.

6.4.3.1 *Surgical Procedures*

Subjects undergoing the following elective open, surgical procedures will be eligible for investigation enrollment:

- Cardiac procedure (Epicardium)
- Cardiac procedure (Aortic Anastomosis or Aortotomy Suture Line);
- Liver resection;
- Total splenectomy;
- On-clamp partial nephrectomy; or
- Radical nephrectomy.

For each of these procedures, a bleeding site meeting intraoperative inclusion/exclusion criteria and whose anatomic site is less than or equal to 25cm² and whose anatomic application site is less than or equal to 47cm², will be evaluated for bleeding flux and satisfaction of the intraoperative eligibility criteria.

For each of these procedures, PerClot should not be allowed to enter into cell saver devices, extracorporeal cardiopulmonary bypass circuits or autologous blood salvage circuits. Granules of PerClot or fragments of gelled PerClot may pass through 40 micron transfusion filters of blood salvaging systems.

For cardiac procedures, the site of evaluation for satisfaction of intraoperative eligibility criteria will be any bleeding sites on the epicardium, along an aortic anastomotic suture line, or an aortotomy suture line. For example, the surgeon will perform dissection of adhesions per his or her conventional methods and bleeding will be controlled using means continually employed by the surgeon prior to surgical closure. Prior to application along an aortic anastomotic suture line or an aortotomy suture line, suture line gaps \geq 2mm and large needle holes \geq 2mm will be ligated prior to assessment of intraoperative eligibility criteria. Any bleeding site on the epicardium, or along an aortic anastomotic suture line, or an aortotomy suture line meeting the eligibility criteria will be evaluated for satisfaction. PerClot should be applied after drug reversal and the patient is taken off by-pass.

For liver resection procedures, the resected liver surface will be the site of evaluation. The surgeon will perform resection of the diseased portion of the liver per his or her conventional methods. Bleeding from discrete vessels will be controlled using means conventionally employed by the surgeon. Vessels \geq 2mm in diameter will be ligated and any observed bile leaks controlled prior to assessment of intraoperative eligibility criteria. Any bleeding site on the exposed parenchymal surface will be evaluated for satisfaction of the eligibility criteria.

For total splenectomy procedures, the site of evaluation for satisfaction of the intraoperative eligibility criteria will be the retroperitoneal surface. The surgeon will perform the splenectomy per his or her conventional methods. Vessels $\geq 2\text{mm}$ in diameter will be ligated prior to assessment of intraoperative eligibility criteria. Any bleeding site on the retroperitoneal surface/cavity will be evaluated for satisfaction of the eligibility criteria.

For on-clamp partial nephrectomies, the site of evaluation will be the kidney bed surface. The surgeon will perform resection of the kidney per his or her conventional methods. Vessels $\geq 2\text{mm}$ in diameter will be ligated and entries into the collecting system controlled prior to assessment of intraoperative eligibility criteria. Any bleeding site on the kidney bed will be evaluated for satisfaction of the eligibility criteria after clamp release.

For radical nephrectomies, the site of evaluation will be the retroperitoneal surface/cavity. The surgeon will perform the procedure per his or her conventional methods. Vessels $\geq 2\text{mm}$ in diameter will be ligated prior to assessment of intraoperative eligibility criteria. Any bleeding site on the retroperitoneal surface/cavity will be evaluated for satisfaction of the eligibility criteria.

A description of the surgical procedure performed, including type of implant of graft used, any concomitant procedures, and bleeding sites to be evaluated will be captured. All conventional method(s) used for hemostasis prior to assessment of intraoperative eligibility criteria will be documented on the Operative eCRF.

6.4.3.2 *Intraoperative Inclusion*

The intraoperative eligibility criteria must be satisfied for the subject to be enrolled and randomized, if applicable, into the investigation.

A subject must meet the following intraoperative eligibility criteria (bleeding severity assessment) to be enrolled into the investigation:

Intraoperative Inclusion Criteria

- Subject is undergoing one of the following open, elective cardiac, general, or urological surgical procedures:
 - Cardiac procedure (Epicardium);
 - Cardiac procedure (Aortic Anastomosis or Aortotomy Suture Line);
 - Liver resection;
 - Total splenectomy;
 - On-clamp partial nephrectomy; or
 - Radical nephrectomy.
- Subject in whom all visible vessels or suture holes, greater than or equal to 2mm in diameter have been ligated, or suture line gaps greater than or equal to 2mm have been ligated;
- Subject in whom there is bleeding at the specified area for each surgical procedure after any applicable conventional means for hemostasis are attempted as specified by the intraoperative protocol;
- Subject in whom the anatomic site is equal to or less than 25cm²;
- Subject in whom the anatomic application site is equal to or less than 47cm²; and
- Subject in whom the bleeding flux from the identified bleeding site is $>0.000040[\text{g}/(\text{cm}^2 \cdot \text{s})]$ and $\leq 0.013[\text{g}/(\text{cm}^2 \cdot \text{s})]$.

Bleeding Severity Score	Bleeding Flux
0=No Bleeding	0-0.000040
1=Ooze	>0.000040-0.0056
2=Slight Bleeding	>0.0056-0.013
3=Moderate Bleeding	>0.013-0.041
4=Severe Bleeding	>0.041-0.063
5=Life-Threatening Bleeding	>0.063

Verbal site description of each score on the bleeding severity scale:

- A score of 0 denotes no active bleeding. The surgical field is completely dry with no blood or the surgical field is stained with blood, but this blood is completely stagnant.
- A score of 1 denotes oozing. The rate of bleeding is slow. This is what one may expect from capillary, venular, or arteriolar bleeding.
- A score of 2 denotes slight bleeding. The rate of bleeding is slightly faster than oozing. There is no pulsatile flow present. This is what one may expect from capillary, venular, or arteriolar bleeding.
- A score of 3 denotes moderate bleeding. There may be a weak pulsatile flow present. If there is a pulsatile flow, the rate of blood flow is similar to the rate of flow for a score of 2. If there is no pulsatile flow, the rate of blood flow is faster than slight bleeding.
- A score of 4 denotes severe bleeding. For the most part, pulsatile flow is present. If there is no pulsatile flow, then the rate of blood flow is extremely rapid.
- A score of 5 denotes life-threatening bleeding. A strong pulsatile flow is always present and the rate of blood flow is extremely rapid.

Intraoperative Exclusion Criteria

- Subject undergoing a cardiac procedure in which there is no aortic anastomosis or aortotomy suture line to evaluate using the bleeding severity scale (i.e., not for treatment at the distal coronary artery bypass graft anastomosis);
- Subject in whom any major intraoperative bleeding incidences during the surgical procedure occurred (i.e., subject with assignment of an American College of Surgeons Advanced Trauma Life Support Hemorrhage Class of II, III, or IV Hemorrhage);
- Subject who has an active or potential infection at the surgical site, or whose surgical wound is defined as a wound classification of CO (Contaminated) or D (Dirty or Infected) based upon the Center for Disease Control and Prevention's wound classification system;^x
- Subject who has undergone platelet receptor GP IIb/IIIa antagonist therapy less than 48 hours prior to surgery.

The surgeon will perform conventional means for hemostasis as specified in Section 6.4.3.1 for the identified bleeding site. Vessels \geq 2 mm in diameter or suture line gaps \geq 2 mm will be ligated.

^x Please see the Glossary (Section 13) for the Center for Disease Control and Prevention's wound classification system.

If there is bleeding that meets the predefined criteria for inclusion in the study, the surgeon will blot the bleeding site with clean gauze to remove blood and any other fluid from the study site; ligate any vessels \geq 2mm diameter or suture line gaps \geq 2 mm. Using a millimeter-incremented tool, measure the 2 longest perpendicular distances of the bleeding site and multiply those two values to calculate the Anatomic Site. Add 1cm to each of the 2 recorded longest perpendicular distances of the bleeding site to calculate Anatomic Application Site. Blot the bleeding site with clean non-weighed gauze before placing 2 of available 10 pre-weighed 4 inch by 4 inch Covidien™ Vistec™ X-ray Detectable sponges, 16 ply (hereinafter referred to as pre-weighed gauze), onto the bleeding site and hold them with gentle pressure (enough to hold the pre-weighed gauze and capture all the blood without deforming the pre-weighed gauze or the tissue) in place until blood is seen on the top layer or for 10 seconds, timed using a timing device that can be stopped in increments of seconds. The stacks of blood-stained gauze will be weighed with the unused gauze and gauze packaging on a pre-calibrated scale (in grams, to 3 decimal places) to determine blood mass collected, and the bleeding flux will be calculated (2 significant digits after the decimal point).

The scale will be calibrated in accordance with the Calibration Plan. Calibration will be documented on the eCRF.

Bleeding Flux [$\text{g}/(\text{cm}^2 \cdot \text{s})$] = [Blood Mass Collected (g)]/ [Anatomic Site (cm^2) · time gauze held (s)]

If the bleeding flux is $> 0.000040[\text{g}/(\text{cm}^2 \cdot \text{s})]$ and $\leq 0.013[\text{g}/(\text{cm}^2 \cdot \text{s})]$, then the subject will be enrolled into the investigation. If the bleeding flux is $\leq 0.000040[\text{g}/(\text{cm}^2 \cdot \text{s})]$ or $> 0.013[\text{g}/(\text{cm}^2 \cdot \text{s})]$, then the subject will not be enrolled into the investigation.

Bleeding flux and site description will be documented on the Operative eCRF.

Confirmation of all the intraoperative eligibility criteria will be documented on the Operative eCRF.

6.4.3.3 *Intraoperative Randomization*

After confirmation of the intraoperative eligibility criteria, the subject will be randomized to receive an adjunct application of PerClot or the control device. The randomization schedule will be stratified by site, therapeutic area and bleeding severity score. Subjects will be randomized on a 1:1 allocation to either PerClot or the control group via envelope randomization. The Randomized Study Device (RSD) will be provided in a manner which will maintain product sterility.

There may be cases in which a subject is randomized but expires before the prescribed hemostatic agent can be applied. In such cases, this will be documented on the screening and enrollment log. Also see Section 6.1.2.

After randomization, the following data will also be collected and documented on the Operative eCRF:

- Identifier number;
- Surgeon;

- Technical failures;
- Diastolic and systolic blood pressure;
- Pulse;
- Core body temperature;
- Use of any blood modifiers, insulin or blood sugar lowering medications; and
- Blood glucose measurement.

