PerClot possesses many of the above-mentioned characteristics of an ideal hemostatic agent. Relevant available preclinical and clinical data, summarized below in Sections 3.1-3.3, demonstrate the safety and efficacy of PerClot. It is derived from plant starch and absorbed within several days of application. Further, there is no risk of infectious disease transmission since none of the components are sourced from animals or humans. Additionally, animal studies have shown that the use of PerClot results in a less severe foreign body response/inflammatory reaction when compared to other hemostatic agents, such as gelatin sponge and bone wax (see Section 3.2). The product is easy to use, with no preparation steps required. PerClot does not work completely independent of native clotting mechanisms, but it forms a gelled, adhesive matrix, which provides a mechanical barrier to further bleeding. The gelled adhesive matrix promotes the normal physiological clotting cascade, resulting from the accumulation of platelets, red blood cells, and coagulation proteins (thrombin, fibrinogen, etc.) at the site of application. A randomized, controlled trial is justified in order to evaluate the safety and efficacy of PerClot compared to another currently approved hemostatic agent in a clinical setting.

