6.2 Investigational and Comparator Devices

6.2.1 *PerClot – Investigational Device*

Please refer to Section 2.

6.2.2 *Comparator Devices*

When a subject is randomized to the control group, he or she will receive Arista on the qualified bleeding site. This hemostatic agent was chosen as the control because it is a medical device, as is PerClot, is plant-based, and does not contain any pharmaceutical components such as thrombin or fibrinogen. Arista has a comparable indication for use as the intended use of PerClot for this clinical trial, and thus would not limit its use in this investigation.

Arista is a medical device intended for application to surgical wound sites as an absorbable hemostat. This technology incorporates hydrophilic, flowable, microporous particles synthesized by cross-linking purified plant starch through a proprietary process; Arista is a 100% plant based polysaccharide. Arista contains no human or animal components. Arista is a fine, dry, sterilized white powder that is biocompatible, non-pyrogenic, and is typically absorbed within 24 to 48 hours.

Arista particles are hydrophilic molecular sieves that enhance natural hemostasis by concentrating blood solids such as platelets, red blood cells, and blood proteins on the particle surfaces to form a gelled matrix. The concentrated gel matrix provides a barrier to further blood loss and is formed regardless of the patient's coagulation status. The concentration of clotting factors and platelets in the gel serves to enhance normal clotting reactions and creates stable hemostatic plugs. The absorption process begins immediately and is dependent on several factors, including the amount applied and site of use.

The use of Arista as the control in this investigation has been approved by FDA.

6.2.3 *Other Medical Devices*

[figure not shown]

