The site of bleeding should be thoroughly covered with the granules. It is important that the PerClot granules come into direct contact with the bleeding surface. Gentle manual pressure will be applied until hemostasis is achieved in accordance with Appendix A: PerClot Instructions for Use and Appendix N: Operative Steps; any gauze used when applying pressure must be carefully removed for hemostasis evaluation. Wetting of the gauze with saline will facilitate this process. If gauze is adhered to the formed blood clot, the gauze should be fully saturated with saline, and then gently and slowly peeled away.

Gentle manual pressure using dry gauze will be applied immediately after application and held for 5 minutes. Gentle manual pressure using dry gauze will be re-applied after the 5 minute hemostatic assessment point and held until the 7 minute evaluation. If at the 7 minute evaluation, hemostasis is achieved, the surgeon will continue to observe the site for an additional 5 minutes (12 minutes post-application) to assess for hemostasis

maintenance. If, at any time after the 7 minute evaluation, hemostasis is not achieved or maintained, the surgeon will be allowed to use alternative measures to control bleeding.

Time of device application will be documented.

The Arista IFU will be followed for the application of control product. Application of Arista will also be addressed during investigator training and in the Operative Steps (Appendix N). The amount of hemostatic product applied in each subject will be determined by recording the mass in grams of the device(s) before and after application.

The surgeon will also be asked to estimate the amount of device left in the patient in relation to the original amount applied (percentage) after saline irrigation and aspiration of excess material, if applicable. The amount of irrigation fluid used during the irrigation and aspiration of excess material will be documented. Dislodgement of RSD, during gauze removal, will be assessed at the 5 minute and 7 minute hemostatic evaluations. The surgeon will document if the dislodgement is perceived to be the sole reason for any observed hemostatic failure. If hemostasis is observed at 7 minutes, maintenance of hemostasis will be assessed for an additional 5 minutes (12 minutes post-application) and again just prior to surgical closure.

Information regarding hemostat application will be documented on Operative eCRF.

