SURGICAL PROCEDURE INFORMATION

1. Surgeon Name:

2. Description of Surgical procedure:

 1 Coronary Artery Bypass Graft (CABG)	 7 Liver Resection
 2 Re-do CABG	 8 Total Splenectomy
 3 Aortic Valve Repair	 9 On-clamp Partial Nephrectomy
 4 Re-do Aortic Valve Repair	 10 Radical Nephrectomy
 5 Mitral Valve Repair	 11 Other, please specify, including type of implant or graft, if applicable: 
 6 Re-do Mitral Valve Repair	

3. Was aspirin use discontinued prior to surgery? 1 Yes 0 No N/A
if yes, how far in advance of surgery was aspirin use discontinued?

4. Please describe any concomitant procedures, if applicable:

BLEEDING SITE INFORMATION

5. Bleeding site to be evaluated (please select one):

 1 Cardiac procedure: epicardium	 6 Cardiac procedure: aortic anastomosis or aortotomy suture line
 2 Liver resection: resected liver surface	
 3 Total splenectomy: retroperitoneal surface	
 4 On-clamp partial nephrectomy: kidney bed	
 5 Radical nephrectomy: retroperitoneal cavity	

6. Conventional means for hemostasis performed before assessment of bleeding (select all that apply):

 1 Suture
 2 Clips
 3 Electrocautery
 4 Argon beam coagulator
 5 Reversal of coagulopathy
 6 Staples
 7 Other, please specify all: 

Subject Initials: Subject Number: Visit Type: ³ Intraoperative

BLEEDING SEVERITY ASSESSMENT					
7. Mass (g) of packaged, sterile gauze:					
8. Mass (g) of 2 packaged 5g bellows – PERCLOT:					
9. Mass (g) of 2 packaged 5g bellows – ARISTA:					

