	
CAUTION: Avoid contacting the applicator tip with blood as this may occlude the applicator. If this occurs, replace applicator tip, if available. If this occurs, and a replacement tip is not available, use a stylus to reestablish the delivery pathway by inserting the stylus through the blocked area. Do not attempt to trim the applicator tip.
 
Do not apply more than the entire contents of up to two 5 gram bellows of PerClot per subject.
	
Discontinue Device-Specific Instructions.		
Continue with the remaining Operative Steps for both PerClot and Arista.		
16	
a. Immediately following application, cover treated site with two clean, sterile, non-weighed gauze. Hold and apply gentle uniform pressure to gauze pads until 5 minutes and 0 seconds.
	
a. Start Timing Device.
 
b. Weigh RSD packaging on a calibrated scale and record.
 
c. Weigh used RSD bellow(s) and applicator tip(s) on a calibrated scale and record.
 
d. Calculate weight of hemostat applied by subtracting the mass measured in steps 16b and 16c from the mass of the pre-weighed packaged study device to which the subject was randomized.

17	
a. At 5 minutes, gently remove gauze by fully saturating gauze with saline and slowly peeling them off as not to dislodge hemostat mass.
	
a. Record actual time at 5 minute assessment.

18	
a. Assess for hemostasis (complete cessation of bleeding).
 
b. Assess for dislodgement of RSD and if primary reason for any observed bleeding.
	
a. Record 5 minute assessment.
 
b. Record if dislodgement of RSD was observed and if primary reason for any observed bleeding.

19	
a. Cover treated site with two clean, sterile, non-weighed gauze. Hold and apply gentle uniform pressure to gauze until 7 minutes and 0 seconds.
	
20	
a. At 7 Minutes, gently remove gauze by fully saturating gauze with saline and slowly peeling them off as not to dislodge hemostatic mass.
	
a. Record actual time at 7 minute assessment.

21	
a. Assess for hemostasis (complete cessation of bleeding).
 
b. Assess for dislodgement of RSD and if primary reason for any observed bleeding.
	
a. Record 7 minute assessment.
 
b. Record if dislodgement of RSD was observed and if primary reason for any observed bleeding.

	Investigator	Coordinator/Surgical Associate

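### In cardiac cases the drug-reversal and bypass condition names only PerClot and is not placed before flux measurement or randomization, so the arms could be treated in different coagulation states

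*Protocol*

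**What the plan says.** The cardiac paragraph of Protocol 6.4.3.1 ends with a timing condition: "PerClot should be applied after drug reversal and the patient is taken off by-pass". It names the investigational device only.

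For the control, Protocol 6.4.3.4 says "The Arista IFU will be followed for the application of control product". Neither that section nor 6.2.2 or 6.4.3.3 gives Arista a condition on reversal or bypass. Appendix N (Operative Steps) carries no such condition for either device.

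On the order of events, Protocol 6.4.3.3 says "After confirmation of the intraoperative eligibility criteria, the subject will be randomized to receive an adjunct application of PerClot or the control device". The criteria in 6.4.3.2 include the bleeding-flux window. None of them requires reversal or separation from bypass. Only the subject is blinded.

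On coagulation, Protocol 6.2.2 says the Arista gel matrix "is formed regardless of the patient's coagulation status", while Protocol Section 3 says "PerClot does not work completely independent of native clotting mechanisms".

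**The concern.** A condition that applies to one device and takes effect only at application can create a difference between arms after randomization. Suppose a cardiac subject is measured and randomized while still anticoagulated or on bypass. Read literally, the protocol asks the surgeon to hold a PerClot application until reversal and separation from bypass. It says nothing to stop an Arista application at once. The surgeon knows the assignment by then.

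Two things would follow. Coagulation state at application would depend on the assigned device, which neither randomization nor stratification can correct. Also, the PerClot subject's qualifying flux, and the severity score used for stratification, would describe a state that no longer holds at treatment, and no step repeats the flux measurement.

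In a non-inferiority comparison, anything that lowers control success relative to PerClot makes a false claim easier. That is the stake, if the sequence occurs and if it acts in that direction.

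**Working it through.** **1. The texts side by side**

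| Place in the Protocol | PerClot | Arista |
|---|---|---|
| 6.4.3.1, cardiac | After reversal and off bypass (worded as *should*) | Nothing |
| 6.4.3.2, eligibility | No reversal or bypass criterion | Same |
| 6.4.3.4, application | Own instructions for use (Appendix A) | Own instructions for use (not supplied) |
| Appendix N, application steps | No reversal or bypass condition | No reversal or bypass condition |

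The partial nephrectomy paragraph of 6.4.3.1 handles a comparable matter differently. It has the bleeding site evaluated for eligibility once the clamp is off. That condition applies to both devices and comes before randomization. The cardiac paragraph lacks this structure. Step 22 of Appendix N contains a cardiac rinsing instruction marked for PerClot recipients only, so a site could reasonably read the PerClot-only sentence in 6.4.3.1 literally.

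**2. The plan's own figure**

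SAP 4.2.1.1 and Appendix A: 154 per arm, 90% in each arm, margin 0.10, one-sided alpha 0.025, Farrington-Manning score test, stated power 0.79885.

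- Restricted estimates under the null, with difference -0.10: about 0.831 and 0.931.
- s0 = √[(0.831×0.169 + 0.931×0.069)/154] ≈ 0.0364.
- s1 = √[(0.9×0.1 + 0.9×0.1)/154] ≈ 0.0342.
- Power = Φ[(0.10 − 1.96×0.0364)/0.0342] ≈ Φ(0.84), which is 0.7988 without rounding the steps. This reproduces the stated figure.

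**3. Illustration of what a difference would do**

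From the documents: about 108 of 324 subjects are cardiac, a share of 0.333 (Protocol 6.6.5). The null boundary is PerClot 80%, control 90%.

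Assumed, because the documents give neither: *f*, the fraction of cardiac Arista subjects treated before reversal or on bypass; and *x*, the change in their success rate.

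Shift in pooled control rate = share × *f* × *x*. The last column is the exact binomial probability that the score test rejects with 154 per arm, PerClot at 0.80 and control at the shifted rate.

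| *f* | *x* | Shift | Control rate | False non-inferiority |
|---|---|---|---|---|
| 0 | any | 0 | 0.900 | 2.5% |
| 0.25 | −0.10 | 0.333×0.25×0.10 = −0.008 | 0.892 | 3.9% |
| 0.50 | −0.10 | 0.333×0.50×0.10 = −0.017 | 0.883 | 5.9% |
| 0.50 | −0.20 | 0.333×0.50×0.20 = −0.033 | 0.867 | 11.9% |
| 0.50 | +0.10 | 0.333×0.50×0.10 = +0.017 | 0.917 | 0.8% |

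The 2.5% baseline is in line with the 2.3% that SAP Table 3 reports for the fixed design at 80% versus 90%; the SAP's code sets PerClot at 0.799 there.

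Protocol 6.6.2 caps any one therapeutic area at 224 of 324 (0.691). If cardiac reached that cap, the second row would become 6.1% and the fourth 34.1%. The cap is a limit, not a forecast for cardiac enrollment.

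**The case against.** The strongest reply is that the sequence needed for harm may never occur. The device is unknown until every intraoperative criterion is confirmed, and Appendix N runs from eligibility through randomization to application without a pause. A surgeon who might draw PerClot has reason to wait for reversal before assessing any cardiac subject, and that would align the arms. The Operative form lists "Reversal of coagulopathy" among the conventional means used before the bleeding assessment, in both arms. Section 6.4.3 adds: "All subjects will undergo the same intraoperative investigational evaluations unless otherwise stated". After application, Appendix N says: "Continue with the remaining Operative Steps for both PerClot and Arista".

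Much of this stands. The documents nowhere describe randomization before reversal. But they do not rule it out either. The reversal entry is an optional tick-box, the shared-evaluation sentence concerns evaluations and not the timing of application, and the shared steps start after the device is on.

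A second reply is that the data would reveal a difference. For reversal this is largely right. The Blood Modifiers form covers reversal drugs with start and stop times, the Operative form asks about blood modifiers between randomization and application, and application time is recorded to the second. Blood modifiers are also a listed covariate (Protocol 6.6.11, SAP 4.6), and treatment by therapeutic area is tested at 0.15 (Protocol 6.6.12, SAP 4.7). Only bypass status has no form item.

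A third reply is that the Arista instructions for use, or investigator training, may carry the same condition. That cannot be checked from the documents. If they do, the asymmetry is in the protocol's wording only.

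**Conclusion.** The gap in the text is certain; its effect on the trial is conditional. The cardiac timing condition names one device, attaches to application, and is not placed before flux measurement or randomization. The protocol as written therefore permits a post-randomization difference in coagulation state in the cardiac stratum, expected to be about one third of subjects.

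Three stronger readings are tempting and not supported:

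- *That PerClot must wait while Arista will be treated under anticoagulation.* The sentence says *should*, and the divergence arises only for subjects randomized before reversal or on bypass. Their number is unknown and may be zero.
- *That the bias favors PerClot.* This is plausible, since a PerClot subject who waits receives reversal, a listed hemostatic measure, after qualifying. It is not established: the protocol describes the Arista gel as insensitive to coagulation status, and with the opposite sign the error rate falls to 0.8%.
- *That reversal status goes unrecorded.* It can largely be derived from the drug and application times.

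The range of 2.5% to 11.9%, or 0.8% with the sign reversed, shows sensitivity under assumed values of *f* and *x*; it does not estimate an expected error rate. The point is worth acting on because the remedy is cheap and the ambiguity affects the primary comparison.

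**What to change.** Reconcile Protocol 6.4.3.1, 6.4.3.4 and Appendix N. Whatever reversal and bypass condition the sponsor adopts should be stated for the Randomized Study Device in both arms, and settled before the flux measurement and the opening of the envelope, as the partial nephrectomy paragraph does with clamp release. This takes no position on which timing is clinically right.

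Add a form item for bypass status at flux measurement and at application. In the SAP, tabulate by arm, for cardiac subjects, reversal relative to application (from existing drug and application times) and bypass status.

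The cost is a few sentences, one form item and one table. Some cardiac sites might have to delay the assessment slightly. No added subjects are needed.
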